Participants who withdraw from further IP injection for any reason after their first IP injection but do not withdraw consent will complete all study procedures through the End of Study (EOS) Visit.

4.2. Statistical Hypotheses

There is no hypothesis testing in this study.

4.3. Sample Size and Power

The sample size for this study is not driven by statistical assumptions for formal hypothesis testing. This sample size is regarded as sufficient to provide an understanding of the safety profile of mRNA-1893 and to select the dose to advance development into future studies.

Approximately 800 participants will be randomly assigned in a 1:1:1:1 ratio to receive 2 doses of µg mRNA-1893 separated by 28 days (Treatment Arm A), 2 doses of µg mRNA-1893 separated by 28 days (Treatment Arm B), a single dose of µg mRNA-1893 on Day 29 following a single dose of placebo on Day 1 (Treatment Arm C), or 2 doses of placebo separated by 28 days (Treatment Arm D). A total of 600 participants will receive mRNA-1893, 200 participants in each dosing arm, with approximately 100 participants in each flavivirus serostatus cohort and dosing arm; approximately 200 participants will receive placebo. Table 2 presents the 95% confidence interval (CI) for 1 participant with an AE and the lowest AE rate detectable with at least 95% probability for each selected sample size. The 2-sided 95% CI was calculated using the Clopper-Pearson

method for one proportion in SAS 9.4 software. A sample size of 200 (or 400) has at least a 95% probability to observe at least 1 participant with an AE at a true 1.49% (or 0.75%) AE rate.

Table 2: 95% Confidence Interval for One Participant with an Adverse Event and the Lowest Detectable Incidence Rate at 95% Probability in Each Selected Sample Size

Sample Size	Rate and 95% CI (%) at One Participant with AE			Lowest Detectable Date (0/)
Receiving mRNA-1893	AE Rate	Lower CI	Upper CI	Lowest Detectable Rate (%) with ≥ 95% Probability
100	1.00	0.03	5.45	2.95
200	0.50	0.01	2.75	1.49
400	0.25	0.01	1.38	0.75
600	0.17	0.00	0.93	0.5

Abbreviations: AE = adverse event: CI = confidence interval.

4.4. Randomization

The randomization will be done in a blinded manner using a centralized Interactive Response Technology (IRT), in accordance with pre-generated randomization schedules. Approximately 800 participants will be randomized in parallel according to a 1:1:1:1 randomization ratio to the 4 treatment arms. Randomization was initially stratified by participants' baseline flavivirus serostatus using a point of care assay under the original protocol (dated 21 February 2021). Under the protocol amendment 1 (16 September 2021), protocol amendment 2 (27 October 2021) and current Amendment 3 (09 December 2021), randomization will be stratified only by participants' region (continental US and Puerto Rico). Only the unblinded pharmacy personnel (Section 4.5) will have controlled access to which arm the participant is randomly assigned.

Blinding and Unblinding This is an observer-blind study. The investigator, study staff, study participants, site monitors, and Sponsor personnel (or its designees) will be blinded to the IP administered until the electronic data capture (EDC) is locked and clinical study report (CSR) has been written, with certain exceptions, please refer to Section 6.3.2 of the protocol for details.

Study site blinded staff will remain blinded to individual treatment assignments until the end of the study.

Except in the case of medical necessity, a participant's treatment assignment should not be unblinded without the approval of the Sponsor. If a participant becomes seriously ill or pregnant during the study, the blind will be broken only if knowledge of the treatment assignment will affect that participant's clinical management. In the event of a medical emergency requiring identification of individual treatment assignment, the investigator will make every attempt to contact the Sponsor medical lead or designee to explain the need for unblinding within 24 hours of opening the code. The investigator will be responsible for documenting the time, date, reason for unblinding, and the names of the personnel involved. The investigator (or designee) will have access to unblind participants within IRT. All unblindings will be tracked via an audit trail in IRT and documented in the final study report.

The Sponsor will remain blinded to IP assignment throughout the treatment phase for each individual treatment arm of the study up until the specified time point for interim analysis (IA), as outlined in Section 6.6.

5. Analysis Populations

The following analysis sets are defined: Randomized Set, Solicited Safety Set, Safety Set, Full Analysis Set (FAS), Per-Protocol (PP) Set.

5.1. Randomized Set

The Randomized Set consists of all participants who are randomized in the study, regardless of the participant's treatment status in the study. Participants will be included in the treatment arm to which they are randomized.

5.2. Solicited Safety Set

The Solicited Safety Set consists of all participants who are randomly assigned and received any IP and contribute any solicited AR data. The Solicited Safety Set will be used for the analyses of solicited ARs and participants will be included in the treatment arm corresponding to the IP they actually received.

5.3. Safety Set

The Safety Set consists of all participants who are randomly assigned and received any IP. The Safety Set will be used for analysis of safety except for the solicited ARs. Participants will be included in the treatment arm corresponding to the IP they actually received.

For Solicited Safety Set and Safety Set, the following rule will be used to determine participant's actual vaccination group:

If a participant only received one injection:

- Participant who received placebo will be summarized under Placebo if the planned treatment arm is also Placebo, otherwise under mRNA-1893 (CCI μg) Single Dose.
- Participant who received mRNA-1893 will be summarized under mRNA-1893 as 2-dose regimen which determined by actual dose received according to the dose range mapping rule below.

If a participant received both injections:

- Participant who received placebo for both injections will be summarized under Placebo.
- Participant who received placebo for the first injection and mRNA-1893 for the second injection will be summarized under mRNA-1893 (CCI μg) Single Dose.
- Participant who received mRNA-1893 as the first injection will be summarized under the higher dose of vaccination group between two injections (eg, Placebo < mRNA-1893 μg < mRNA-1893 μg) according to the dose range mapping rule below.

If non-protocol mRNA-1893 dose level occurs, below dosing range mapping rule will be used:

- mRNA-1893 μ g: If the received dose of mRNA-1893 is $> 0 \mu$ g and $\leq 65 \mu$ g.
- mRNA-1893 μ g: If the received dose of mRNA-1893 is > 65 μ g.

5.4. Full Analysis Set

Full Analysis Set (FAS) for Antibody-Mediated Immunogenicity

The FAS for antibody-mediated immunogenicity consists of all randomized participants who

- a) receive any study vaccination,
- b) have baseline (Day 1) antibody-mediated immunogenicity data available for those analyses that require baseline data, and

Statistical Analysis Plan, Version 2.0

Date Issued: 19 April 2023

c) have at least one post-vaccination antibody-mediated immunogenicity assessment for the analysis endpoint.

FAS for Cell-Mediated Immunogenicity

The FAS for cell-mediated immunogenicity (CMI) consists of all randomized participants who

- a) receive any study vaccination,
- b) have baseline (Day 1) CMI data available for those analyses that require baseline data, and
- c) have at least one post-vaccination CMI assessment for the analysis endpoint.

Participants will be included in the vaccination group to which they are randomized.

5.5. Per-Protocol Sets

The Per-Protocol (PP) Set for Antibody-Mediated Immunogenicity

PP Set for Antibody-Mediated Immunogenicity consist of all FAS participants who

- a) comply with the vaccination schedule,
- b) comply with the timings of immunogenicity blood sampling to have post-vaccination results available for at least one assay component corresponding to the immunogenicity analysis objective (antibody-mediated immunogenicity endpoints), and
- c) have no major protocol deviations that impact immune response during the period corresponding to the immunogenicity analysis objective (antibody-mediated immunogenicity endpoints).

The PP Set for Antibody-Mediated Immunogenicity will serve as the primary population for the analysis of antibody-mediated immunogenicity data in this study. Participants will be included in the vaccination group to which they are randomized.

PP Set for CMI

PP Set for CMI consist of all FAS for Cell-Mediated participants who

- a) comply with the vaccination schedule,
- b) comply with the timings of immunogenicity blood sampling to have post-vaccination results available for at least one assay component corresponding to the immunogenicity analysis objective (CMI endpoints), and

c) have no major protocol deviations that impact immune response during the period corresponding to the immunogenicity analysis objective (CMI endpoints).

The PP Set for CMI will serve as the primary population for the analysis of CMI data in this study. Participants will be included in the vaccination group to which they are randomized.

Participants who did not take blood sample for immunogenicity within [21, 42] days after the second injection date will be excluded from the Per-Protocol Set. Participants who only received 1 dose or who received the second dose outside of the window [21, 42] will be excluded from the Per-Protocol Set.

6. Statistical Analysis

6.1. General Considerations

The Schedule of Assessments is provided in Appendix E for the vaccination period and the follow-up period, and Appendix F for the extension period.

Continuous variables will be summarized using the following descriptive summary statistics: the number of subjects (n), mean, standard deviation (SD), median, minimum (min), and maximum (max).

Categorical variables will be summarized using counts and percentages.

Baseline value, unless specified otherwise, is defined as the most recent non-missing measurement (scheduled or unscheduled) collected before the first dose of IP. For immunogenicity tests, the baseline is defined as the most recent non-missing measurement (scheduled or unscheduled) collected before or on the date of first dose of IP.

For the summary statistics of all numerical variables unless otherwise specified, the display precision will follow programming standards. Please see Appendix A for variable display standards.

When count data are presented, the percentage will be suppressed when the count is zero in order to draw attention to the non-zero counts. A row denoted "Missing" will be included in count tabulations where specified on the shells to account for dropouts and missing values. The denominator for all percentages will be the number of subjects in that vaccination group within the analysis set of interest, unless otherwise specified.

Study day relative to the first injection will be calculated as below:

a) study day prior to the first injection will be calculated as: date of assessment/event
 date of the first injection;

b) study day on or after the date of the first injection will be calculated as: date of assessment/event – date of the first injection + 1;

Study day relative to the most recent injection will be calculated as below:

- a) study day prior to the first injection will be calculated as: date of assessment/event
 date of the first injection;
- b) study day on or after the date of the first injection but before the second injection (if applicable) will be calculated as: date of assessment/event date of the first injection + 1;
- c) study day on or after the date of the second injection will be calculated as: date of assessment/event – date of the second injection + 1; if study day is on the same day as the second injection, date and time will be compared with the second injection date and time.

For calculation regarding antibody titers/antibody concentrations, antibody values reported as below LLOQ will be replaced by 0.5 × LLOQ. Values that are greater than the upper limit of quantification (ULOQ) will be converted to the ULOQ. Missing results will not be imputed.

The following stages for safety analyses will be used in this study:

- Up to 28 days after any vaccination: this stage starts at the day of each vaccination
 and continue through the earliest date of (the day of each vaccination and 27
 subsequent days, next vaccination [if applicable]). This analysis period will be used
 as the primary analysis period for safety analyses including unsolicited AE, except
 for solicited AR, unless specified otherwise.
- Up to 28 days after the first vaccination.
- Up to 28 days after the second vaccination.
- Overall stage: this analysis period starts at the first injection on Day 1 and continues through the earliest date of (study completion, discontinuation from the study, or death).

Unscheduled visits: Unscheduled visit measurements will be included in analysis as follows:

- In scheduled visit windows per specified visit windowing rules.
- In the derivation of baseline/last on-treatment measurements.
- In the derivation of maximum/minimum on-treatment values and maximum/minimum change from baseline values for safety analyses.
- In individual subject data listings as appropriate.

Visit windowing rules: The analysis visit windows for protocol-defined visits are provided in Appendix B.

Incomplete/missing data:

- Imputation rules for missing prior/concomitant medications, non-study vaccinations and procedures are provided in Appendix C.
- Imputation rules for missing AE dates are provided in Appendix D.
- For laboratory assessments, if majority of results are indefinite, imputation of these values will be considered. If the laboratory results are reported as below the LLOQ (e.g., <0.1), the numeric values will be imputed by 0.5 × LLOQ in the summary. If the laboratory results are reported as greater than the ULOQ (e.g., >3000), the numeric values will be imputed by ULOQ in the summary.
- Other incomplete/missing data will not be imputed, unless specified otherwise.

Treatment groups:

The following vaccination groups will be used for summary purposes:

- mRNA-1893 vaccine: μg (2-dose)
- mRNA-1893 vaccine: CCI μg (2-dose)
- mRNA-1893 vaccine: μg (single-dose)
- mRNA-1893 vaccine: Total
- Placebo

Summary by flavivirus serostatus:

All analyses and data summaries/displays will be provided by flavivirus serostatus (flavivirus-seropositive, flavivirus-seronegative, and/or overall) unless otherwise specified,

please also refer to Section 6.5 Planned Analyses. Baseline flavivirus status is determined by serology testing.

A participant is baseline seronegative if at least three baseline serology testings (dengue IgG, dengue IgM, West Nile IgG and West Nile IgM) are negative, and none of the serology testings is positive. If at least one of the baseline serology testings is positive, the participant is baseline seropositive. If two or more of the serology testings are "missing" or "unknown", and none of the serology testings is positive, the baseline serostatus will be "unknown" or "missing". A single testing result of "equivocal" is considered as "unknown", regardless of the numeric values.

All analyses will be conducted using SAS Version 9.4 or higher.

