6.4. Investigational Product Compliance

All doses of IP will be administered at the study site under direct observation of unblinded pharmacy personnel and appropriately recorded (date and time) in the electronic case report forms (eCRFs). Unblinded pharmacy personnel will confirm that the participant has received the entire dose of IP. If a participant does not receive IP or does not receive all of the planned doses, the reason for the missed dose will be recorded.

Participants who miss the second vaccination due to noncompliance with the visit schedule will still be required to follow the original visit and testing schedule as described in the protocol. Unless consent is withdrawn, a participant who withdraws or is withheld from receiving the second dose of IP will remain in the study and complete all safety and immunogenicity assessments required through the scheduled EOS.

The study site is responsible for ensuring participants comply with the study windows allowed. If a participant misses a visit, every effort should be made to contact the participant and complete a visit within the defined time window (Table 1 and Table 2). If a participant does not complete a visit within the time window, that visit will be classified as a missed visit and the participant will continue with subsequent scheduled study visits. All safety requirements of the missed visit will be captured and included in the subsequent visit (eg, eDiary review for reactogenicity, immune testing, as applicable).

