- Solicited local and systemic ARs (Section 11.2.3; Appendix 2) that occur on the day of each dose and during the 7 days after injection (ie, the day of injection and 6 subsequent days). Any solicited AR that is ongoing beyond Day 7 will be recorded until it is no longer reported, not to exceed 28 days after each injection. Solicited ARs recorded in eDiaries beyond Day 7 should be reviewed by study site staff either during the next scheduled telephone call or at the next study site visit (Table 1 and Table 2).
- Daily oral body temperature measurement should be performed at approximately the same time each day using the thermometer provided by the study site. If body temperature is taken more than once in a given day, only the highest temperature reading should be recorded.
- Measurements, as applicable, for solicited local ARs (injection site erythema and swelling/induration); the size measurements will be performed using the ruler provided by the study site.
- All medications taken on the day of each dose and during the 28 days after injection (ie, the day of injection and 27 subsequent days). Participants will be queried by the eDiary whether any medications were taken to treat or prevent pain or fever on a day of injection or for the 6 subsequent days.

The eDiaries will be the main source documents allowed for solicited local or systemic ARs (including body temperature measurements). Participants will be instructed to complete eDiary entries daily. If assessments are not recorded for a given day, the participant will have a limited time window on the following day to complete qualitative assessments for the previous day, excluding measurements of body temperature and of any injection site erythema or swelling/induration. Any new safety information reported during safety telephone calls or at site visits (including a solicited AR) not already captured in the eDiary will be described in the source documents as a verbally reported event. Any solicited AR reported in this manner must be entered on the Reactogenicity page of the eCRF.

Procedures for transferring eDiary data to the eCRF are presented in the Study mRNA-1893-P201 Study Manual. Study site staff will review eDiary data with participants at the Day 8 and Day 36 Visits.

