6.3.1. Adverse Events

An AE is defined as any untoward medical occurrence in a subject or clinical investigation subject who is administered a pharmaceutical product at any dose that does not necessarily have to have a causal relationship with the treatment.

A treatment-emergent AE (TEAE) is defined as any event occurring during the study not before exposure to study vaccine or any event already present that worsens after exposure to study vaccine. Adverse events will also be evaluated by the investigator for the coexistence of MAAE which is defined as an AE that leads to an unscheduled visit to a healthcare practitioner.

Unsolicited AEs will be coded by PT and SOC using MedDRA summarized by baseline flavivirus serostatus, vaccination group, and stage (up to 28 days after each vaccination, up to 28 days after any vaccination and overall stage; see Section 6.1 for definitions of vaccination group and stage).

All summary tables (except for the overall summary of AEs) for unsolicited AEs will be presented by SOC and PT for TEAEs with counts of subjects included. SOC will be displayed in internationally agreed order. PT will be displayed in descending order of frequency of total mRNA-1893 and then alphabetically within SOC. When summarizing the number and percentage of subjects with an event, subjects with multiple occurrences of the same AE or a continuing AE will be counted once. Subjects will be presented according to the highest severity (the strongest relationship) in the summaries by severity (of related AEs), if subjects reported multiple events under the same SOC and/or PT.

Percentages will be based upon the number of subjects in the Safety Set within each vaccination group.

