6.3.1.5. Solicited Adverse Reactions

All summary tables for solicited ARs will be provided by baseline flavivirus serostatus (flavivirus-seropositive, flavivirus-seronegative, and/or overall).

An AR is any AE for which there is a reasonable possibility that the test product caused the AE. The term "Solicited Adverse Reactions" refers to selected signs and symptoms occurring after injection administration during a specified post-injection follow-up period (day of injection and 6 subsequent days). The solicited ARs are recorded by the subject in eDiary. The occurrence and intensity of selected signs and symptoms is actively solicited from the participant during a specified post-injection follow-up period (day of injection and 6 subsequent days), using a pre-defined checklist in the eDiary (i.e., solicited ARs).

The following local ARs will be solicited: pain at injection site, erythema (redness) at injection site, swelling (hardness) at injection site.

The following systemic ARs will be solicited: headache, fatigue, myalgia (muscle aches all over the body), arthralgia (aching in several joints), nausea/vomiting, fever, and chills.

The solicited ARs will be graded based on the grading scales presented in Table 13 in the protocol, modified from the Toxicity Grading Scale for Healthy Adult and Adolescent Volunteers Enrolled in Preventative Vaccine Clinical Trials (DHHS 2007). Investigator will assess Grade 4 events (with exception of fever).

If a solicited local or systemic AR continues beyond 7 days post injection, the participant will be prompted to capture solicited local or systemic AR in the eDiary until resolution.

All solicited ARs (local and systemic) will be considered causally related to vaccination.

All solicited ARs analyses will be based on Solicited Safety Set. All solicited ARs analyses will be provided by flavivirus serostatus and vaccination group as defined in Section 6.1 for each vaccination (first, second), unless otherwise specified.

The number and percentage of subjects who reported any solicited AR, any solicited local AR, and any systemic solicited AR during the 7-day follow-up period after each vaccination will be tabulated by flavivirus serostatus, vaccination group, and vaccination,

with a two-sided 95% exact CI using the Clopper-Pearson method. The same analysis will be conducted for subgroups defined by region (United States and Puerto Rico).

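### Unless the table shells say otherwise, second-injection safety percentages are taken over a set that includes participants who never received that injection

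*SAP*

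**What the plan says.** **Default base.** SAP 6.1: "The denominator for all percentages will be the number of subjects in that vaccination group within the analysis set of interest, unless otherwise specified".

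**Unsolicited AEs.** SAP 6.3.1 gives an explicit base: "Percentages will be based upon the number of subjects in the Safety Set within each vaccination group". The same section summarizes these events by stage, and one stage listed in SAP 6.1 is "Up to 28 days after the second vaccination".

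**Solicited ARs.** SAP 6.3.1.5 bases all these analyses on the Solicited Safety Set, "provided by flavivirus serostatus and vaccination group as defined in Section 6.1 for each vaccination (first, second), unless otherwise specified", with exact Clopper-Pearson intervals for the any-AR summaries. SAP 5.2 defines that set: "The Solicited Safety Set consists of all participants who are randomly assigned and received any IP and contribute any solicited AR data". Data after the first injection are therefore enough for membership.

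**One-injection participants.** SAP 5.3 has a rule that assigns them to a group, so they belong to the safety sets by design. For those given only placebo: "Participant who received placebo will be summarized under Placebo if the planned treatment arm is also Placebo, otherwise under mRNA-1893", with the text continuing to the single-dose group. Protocol 6.4 keeps them under observation: unless consent is withdrawn, "a participant who withdraws or is withheld from receiving the second dose of IP will remain in the study".

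**Analysis sets.** SAP 5 lists five sets, none tied to a particular injection. Neither document limits a second-injection denominator to people who received that injection.

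**The concern.** A participant who never received the second injection cannot appear in the numerator of a second-injection percentage but, under the stated rules, stays in the denominator. The exact interval also treats that person as an observed non-event. Missed injections can therefore only lower these rates.

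Solicited ARs after each injection are a primary safety endpoint, and the Day 57 interim analysis is the basis for moving to Phase 3. The single-dose arm needs particular care. Its Day 1 injection is placebo, so the Day 29 injection is the only vaccine exposure. The SAP 5.3 rule puts a placebo-only recipient from that arm into the single-dose group, where that person counts as a vaccinee without a reaction.

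**Working it through.** **1. The plan's nearest figure.** The documents give no number for a second-injection denominator. The closest is SAP Table 2, the lowest AE rate with at least a 95% chance of one or more events: 1 - 0.05^(1/n).
- n = 200: 1.487%, stated as 1.49%.
- n = 400: 0.746%, stated as 0.75%.

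Both reproduce. If only 190 or 180 of 200 receive the injection, the same formula gives 1.56% or 1.65%.

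**2. Effect of the denominator.** Let N be the number in the set for a group, n2 the number who received the second injection, x the number with the event after it, and m = 1 - n2/N.

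Reported rate = x/N = (x/n2) × (n2/N) = recipients' rate × (1 - m).

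This holds for solicited ARs and for the second-injection stage of unsolicited AEs.

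**3. Size.** The documents give no m, so 2%, 5% and 10% are assumptions. The illustrative rate of 45.5% is a second-injection fatigue rate quoted in Protocol 2.3.2.
- m = 2%: 45.5 × 0.98 = 44.6%
- m = 5%: 45.5 × 0.95 = 43.2%
- m = 10%: 45.5 × 0.90 = 41.0%
- m = 0: no change

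For the single-dose group, with a first-vaccination headache rate of 21.7% from the same section as illustration and m = 5%: 21.7 × 0.95 = 20.6%.

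**4. Against sampling error.** Whole-number counts near that rate, planned N = 200, Clopper-Pearson 95% CI:

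| Assumed m | Over recipients | Over the whole set | Shift (points) |
|---|---|---|---|
| 2% | 90/196 = 45.9% (38.8 to 53.2) | 90/200 = 45.0% (38.0 to 52.2) | 0.9 |
| 5% | 87/190 = 45.8% (38.6 to 53.2) | 87/200 = 43.5% (36.5 to 50.7) | 2.3 |
| 10% | 82/180 = 45.6% (38.1 to 53.1) | 82/200 = 41.0% (34.1 to 48.2) | 4.6 |

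The half-width is about 7.1 points, for example (50.7 - 36.5)/2, so each shift is smaller. In a serostatus cell of 100 at m = 5%, 44/95 = 46.3% (36.0 to 56.8) becomes 44/100 = 44.0% (34.1 to 54.3).

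**5. What is not affected.**
- The any-vaccination and overall stages: every member of the safety sets received at least one injection.
- Per-Protocol immunogenicity: SAP 5.5 excludes one-dose participants.
- The vaccine-to-placebo ratio of rates, if m is equal across arms: (1 - m) cancels.

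**6. Choosing the solicited AR base.** Protocol 8.5.1 says of verbally reported reactions: "Any solicited AR reported in this manner must be entered on the Reactogenicity page of the eCRF". It describes no matching entry for the absence of a reaction. If that page could qualify a recipient for the denominator, people without a diary would enter only when they had a reaction. With true rate r, share d without a diary, and all their reactions reported verbally, the rate becomes r / (1 - d(1 - r)). For r = 45.5% and an assumed d = 10%: 0.455 / (1 - 0.10 × 0.545) = 48.1%. That is 2.6 points too high, slightly more than the 2.3-point shift at m = 5% in the table. With no verbal reports this bias is zero.

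**The case against.** **The solicited AR rule is a default that can be overridden.** SAP 6.1 allows exceptions, and the table shells, which hold further detail, were not available. The default does not name serostatus either, yet it must be applied within serostatus, so the by-vaccination layout could be read as implying its own n. This stands as a limit on certainty for solicited ARs. It is weaker for unsolicited AEs, where SAP 6.3.1 states the whole Safety Set as the base.

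**The effect is small and visible.** It may be zero, and SAP 6.2.1 tabulates how many received each dose by serostatus and group, so a reader can rescale. This largely stands. However, that table is by randomized arm while the safety tables are as treated, so the rescaling is approximate, and the printed intervals stay uncorrected.

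**Stronger readings the documents do not support.**
- A reader might infer from Protocol 2.3.2 that Phase 1 used injection-specific denominators (23, then 22, at one dose level), that this study would be on a different base, and that 1/23 = 4.3% estimates the share who miss the injection. The listed symptom rates do fit those counts. But the fever figure printed with its count, apparently for the same level (dose labels are blacked out), does not: 12.6% with 3 cases, against 3/22 = 13.6%, 3/23 = 13.0% and 3/24 = 12.5%. A fall from 23 to 22 could also mean missing data rather than a missed injection. The SAP specifies no comparison with Phase 1 rates.
- A reader might infer that the comparison with placebo is biased. That requires unequal loss between arms, which nothing in the documents shows.

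**Conclusion.** The point holds as a defect in the stated rules, of modest and unknown size. Read literally, SAP 6.3.1 for unsolicited AEs and the SAP 6.1 default for solicited ARs count people never given the second injection as non-events after it. The rate falls by exactly the factor (1 - m), and the exact interval moves down with it. In the single-dose group this dilutes the rate for the only vaccine injection with people never given mRNA-1893.

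At assumed m up to 10% and 200 per arm, the shift stays below the interval half-width. It runs in one direction, however, and a larger sample would not remove it. The conclusion rests on the SAP text without the table shells: if these already set an injection-specific n, only the SAP wording needs to be brought into line. It should be corrected because it concerns a primary safety endpoint and is cheap to settle, but it does not put the study's conclusions in doubt.

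**What to change.** State in SAP 5.2, 6.1, 6.3.1 and 6.3.1.5 that:
- unsolicited AE percentages for the stage after the second vaccination use participants who received the second injection;
- by-injection solicited AR percentages and their Clopper-Pearson intervals use participants who received that injection and have eDiary data after it;
- recipients without eDiary data after that injection, and reactions reported only verbally through the Reactogenicity page, are shown separately, so that entry to the denominator does not depend on having a reaction;
- the overall Safety Set and Solicited Safety Set remain the base for any-injection summaries.

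The table shells should carry the same n. The cost is a few lines of SAP text, two population flags (received the injection; eDiary data after it) and the separate counts. The downside is slightly higher second-injection rates and a different n for the first and second injections. The eDiary base also assumes that not completing a diary is unrelated to having a reaction; the separate counts let a reader judge that.
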